5.3 Risks of long-acting corticosteroid injections

Corticosteroids rapidly decrease the numbers and function of peripheral lymphocytes and inflammatory cytokines. Short term, high dose IM injections are generally well tolerated, but it is important to monitor for HTN, fluid retention and common psychiatric side effects including insomnia and agitation. The potential side effects of corticosteroids are well documented and familiar to the lupus clinic. Although the temporary use of steroid injections used in this protocol is not likely to lead to many side effects, it is important for all study staff to be familiar with them and is good clinical practice. Discussions about minimizing steroids will take place with all participants with SLE, who suffer significant morbidity over the many years of illness from these extremely useful but chronically toxic medications.

Potential risk of long term corticosteroid use may result in cardio-renal side effects such as elevation of blood pressure, increased excretion of potassium, and increased calcium excretion; endocrine side effects such as hypothalamic-pituitary adrenal axis suppression, Cushing's syndrome, and hyperglycemia; dermatological side effects such as acne, striae, thin parchment skin, and easy bruising; ophthalmic side effects such as posterior subcapsular cataracts, glaucoma with possible damage to the optic nerves, and enhanced risk of secondary ocular infections; weight gain; moon facies; increased susceptibility to infections, and osteoporosis. In addition, glucocorticoids can cause dyslipidemia, heart disease, fluid retention, gastrointestinal bleeding and neuropsychiatric effects like mood disorders and psychosis. Many of the risks are for corticosteroid use in general and may not be applicable for the short periods before randomization and re-randomization for which this treatment will be used.

Risks of intramuscular administration of methylprednisolone acetate cited below are noted in the United States Prescribing Information for DEPO-MEDROL® (methylprednisolone acetate injectable suspension, USP) from 2018.

Contraindications:

- Methylprednisolone acetate is contraindicated in patients with known hypersensitivity to the product and its constituents.
- Methylprednisolone acetate is contraindicated in systemic fungal infections, except when administered as an intra-articular injection for localized joint conditions.
- Administration of live or live, attenuated vaccines is contraindicated in patients receiving immunosuppressive doses of corticosteroids.

With the use of triamcinolone acetonide IM, there is a risk of subcutaneous fat atrophy and hypopigmentation which can be minimized by intramuscular injection into the gluteal muscle using at least a 1 1/2 inch needle [72].

5.4 Risks of Withdrawal of Lupus Medications

During Stage 1, consenting participants will withdraw from current lupus medications. Withdrawal of lupus medications per protocol prior to randomization into Stage 2 could lead to disease exacerbation or flare. After signing of consent, the participant will receive a corticosteroid injection, which may be repeated an additional 2 times to achieve amelioration of symptoms. The use of corticosteroid injections which naturally wane in their effects gradually is a mitigation strategy for these risks.

5.5 Special Considerations for COVID-19 or Other Public Health Emergency

Clinical trial conduct may be impacted by the COVID-19 or other infectious disease public health emergency. Infectious disease screening or testing procedures mandated by local health authorities or the health system where the clinical trial is conducted may be performed without the need for a protocol amendment. In certain cases, the participants may not be able to come to the study site, or local institutional policies or other factors may limit access to the research site. The sponsor, study team, and site investigator will determine if alternative methods for conducting assessments and procedures are necessary and feasible, for example telemedicine. The safety of participants is paramount.

Participants will be educated regarding the risk of the infectious disease, and about public health recommendations for precautions.

5.6 Potential Benefits

For Stage 2 (randomization to MMF or corresponding placebo MMF), one or more baseline immunophenotypes may be associated with treatment success (or failure). This knowledge could set the stage for future studies to establish biomarkers that inform treatment option decisions.

Voclosporin, in combination with MMF, has shown benefit in LN. Although it has not been evaluated in SLE without LN, participants treated with voclosporin plus MMF in Stage 3 (randomization to voclosporin plus MMF or MMF alone) may experience a longer period of symptom relief when compared to participants who receive MMF alone.

The knowledge gained from this study may advance our understanding of how molecular and gene expression profiles relate to treatment success (or failure) and suggest strategies for personalized medicine for future study.

6 Investigational Agent

6.1 Investigational Agents

6.1.1 MMF and Placebo for MMF

6.1.1.1 Formulation, Packaging, and Labeling

MMF is an antimetabolite immunosuppressant [28]. It is the 2-morpholinoethyl ester of MPA, an immunosuppressive agent; inosine monophosphate dehydrogenase (IMPDH) inhibitor. The chemical name for MMF is 2-morpholinoethyl (E)-6-(1,3-dihydro-4-hydroxy-6-methoxy-7-methyl-3-oxo-5-isobenzofuranyl)-4-methyl-4-hexenoate. MMF is a white to almost white crystalline powder. It is slightly soluble in water (43 mcg/mL at pH 7.4), freely soluble in acetone, soluble in methanol, sparingly soluble in anhydrous ethanol [28].

Commercially available MMF (250 mg capsules) manufactured by Sandoz will be purchased by NIAID Investigational Product Procurement Center, and overencapsulated, rebottled, blind labeled, packaged, and distributed by DAIT/NIAID Clinical Product Center (CPC) to site investigational pharmacies.

Placebo for MMF will be manufactured by DAIT CPC and will not contain active ingredients. Both MMF and placebo for MMF will be overencapsulated to blind MMF/Placebo capsules.

6.1.1.2 Dosage, Preparation, and Administration

MMF and matching placebo for MMF will be provided in 250mg overencapsulated gel capsules and will be administered orally. The blinded overencapsulated MMF/Placebo capsules should not be opened or crushed. Avoid inhalation or direct contact with skin or mucous membranes of the powder contained in blinded overencapsulated MMF/Placebo capsules.

Blinded overencapsulated MMF/Placebo should be stored at 20° to 25°C (68° to 77°F).

Stage 2 Dosing:

- **Week 1:** Participants will receive 500mg MMF/Placebo twice daily
- **Week 2:** Participants will receive 500mg/Placebo in the morning and 1,000mg MMF/Placebo in the evening
- **Weeks 3-48:** Participants will receive 1000mg MMF/Placebo twice daily

Stage 3 Dosing: (Individuals who received placebo MMF in Stage 2)

- **Week 1:** Participants will receive 500mg MMF plus matching placebo for MMF (to appear like a 1000mg dose) twice daily
- **Week 2:** Participants will receive 500mg plus matching placebo for MMF (to appear like a 1000mg dose) and 1000mg in divided doses
- **Weeks 3-24:** 1000mg MMF twice daily

Participants who received MMF in Stage 2

- **Week 1-24:** 1000mg MMF twice daily

6.1.2 Voclosporin and Placebo for Voclosporin

6.1.2.1 Formulation, Packaging, and Labeling

Voclosporin is a calcineurin-inhibitor immunosuppressant [21]. Chemically, voclosporin is named: Cyclo{[(6E)-(2S,3R,4R)-3-hydroxy-4-methyl-2-(methylamino)-6,8-nonadienoyl]-L-2-aminobutyryl-N-methyl-glycyl-N-methyl-L-leucyl-L-valyl-N-methyl-L-leucyl-L-alanyl-D-alanyl-N-methyl-L-leucyl-N-methyl-L-leucyl-N-methyl-L-valyl]. It appears as white to off-white solid matter. At ambient temperature, voclosporin is freely soluble in acetone, acetonitrile, ethanol, and methanol, and practically insoluble in heptanes (USP). Voclosporin is practically insoluble (less than 0.1 g/L at 20°C) in water and melts above 144°C with decomposition [21].

The manufacturer Aurinia Pharmaceuticals will supply LUPKYNIS™ (voclosporin) 7.9 mg gel capsules and placebo for voclosporin. Placebo capsules do not contain active ingredients.

DAIT CPC will label and distribute active voclosporin and placebo for voclosporin to the clinical site pharmacies. Clinical site pharmacies will dispense voclosporin/placebo to participants as required per arm of Stage 3.

6.1.2.2 Dosage, Preparation, and Administration

Voclosporin will be provided in 7.9 mg gel capsules for oral administration. Placebo for Voclosporin will be provided as gel capsules for oral administration.

The rate and extent of voclosporin absorption is decreased on co-administration with food, therefore, to maximize absorption it is recommended that voclosporin is administered on an empty stomach.

Voclosporin should be stored at 20° to 25°C (68° to 77°F).

Stage 3 Dosing:

- **Weeks 1-24:** 23.7 mg Voclosporin/Placebo (3 x 7.9 capsules) twice daily

Voclosporin/Placebo dose may be modified for renal impairment, see Section 6.4.7, *Decreases in eGFR*.

- Allowed voclosporin/placebo dose reductions include: 15.8 mg or Placebo (2 capsules) orally twice daily and 7.9 mg or Placebo (1 capsule) orally twice daily.

6.2 Drug Accountability

Under Title 21 of the Code of Federal Regulations (21CFR §312.62), the investigator will maintain adequate records of the disposition of the investigational agents, including the date and quantity of the product(s) received, to whom the product(s) was dispensed (participant-by-participant accounting), and a detailed accounting of any product(s) accidentally or deliberately destroyed. Details of investigational product(s) distribution to each participating clinical site will be maintained by the DAIT CPC. The investigator must delegate the drug accountability responsibility to a licensed/registered pharmacist at registered investigational pharmacy at the clinical research site. Please refer to the DAIT Pharmacy Guidelines (<https://www.niaid.nih.gov/sites/default/files/pharmacy.pdf>).

All personnel involved in drug management and preparation must receive proper training based on the DAIT and site requirements prior to study initiation. The Pharmacist of Record should be listed on the Delegation of Responsibility Log (DoR) and is responsible to ensure that any pharmacy personnel involved in any aspect of the drug management, preparation, and dispensing process have completed and documented all DAIT required trainings (Good Clinical Practice (GCP)/Human Subject Protection (HSP), protocol/pharmacy manual, DAIT Pharmacy Guidelines). Only individuals listed on the DoR log and/or the Investigator of Record Agreement (IORA) may manage drug products for this study. All drug disposition and dispensing (receipt, storage, use, return, and disposition) will be maintained by the study site using investigation product(s) and/or placebo-accountability and participant-specific dispensing logs that are approved by DAIT/NIAID and 21 CFR Part 11 compliant. This log will contain the identification of each participant and the date and quantity of investigational product(s) dispensed.

The study clinical research associate (CRA) will conduct accountability of the drugs by monitoring the main Accountability Records and Participant-Specific Accountability logs. The study CRA will also review other pharmacy logs, as applicable. All records regarding the disposition of the investigational product(s) will be available for monitoring and inspection. At the termination of the study, all unused product(s) (expired or un-expired) will be returned to DAIT CPC. For more detailed information on handling of the investigational product(s), please refer to the Pharmacy Manual.

6.3 Assessment of Participant Compliance with Investigational Agents

The number of capsules of study product returned to the site will be counted and recorded at all clinic visits. Participants will also be given a diary to record episodes of intolerance or reasons why a pill may not have been taken.

6.4 Toxicity Prevention and Management

6.4.1 Hypersensitivity

Individuals with known hypersensitivity MMF, MPA, any component of MMF, Polysorbate 80 (Tween), long-acting corticosteroid preparations or their constituents, or voclosporin or its constituents will be excluded from participation in the trial.

6.4.2 Reproductive Risks

Women on MMF are at increased risk of first trimester pregnancy loss and congenital malformations in children. Data on pregnancy risk is unavailable for voclosporin. Women of childbearing potential will have a pregnancy test at each study visit. Should pregnancy occur, study medications will be discontinued immediately, study visits will continue as scheduled except for study medication, and the pregnancy will be followed per Section 12.6, *Pregnancy Reporting*. Appropriate referrals should be made for counseling on fetal effects of study medication. The pregnancy should be reported to the Mycophenolate Pregnancy Registry, which is a part of the MMF REMS program. Male participants and female partners capable of becoming pregnant are encouraged to use a contraceptive barrier method during the study.

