3.1.2 Stage 2: Randomization

One hundred and twenty qualifying participants who withdraw from treatment as described in protocol Section 3.1.1, *Stage 1: Treatment Withdrawal*, and meet improvement criteria for randomization as outlined in Section 4.2.2, *Inclusion criteria required prior to randomization*, will be randomized (1:1) to receive up to 48 weeks of either MMF or corresponding MMF placebo. For the first 2 weeks, a scheduled “taper-up” of MMF will take place. Participants will receive 500 mg MMF (or corresponding MMF placebo) BID for 7 days, followed by 500mg and 1,000mg MMF (or corresponding MMF placebo) in divided doses for 7 days. They will then continue at a stable dose of 1,000mg MMF (or corresponding MMF placebo) BID. Visits to evaluate AEs, vital signs, hematology and chemistry, study medication compliance, medication use, disease status, participant reported outcomes, and to obtain biomarker samples will occur every 4 weeks after randomization.

Participants will be followed for a maximum of 48 weeks on study-provided medication in Stage 2. If a participant experiences an increase in SLE symptoms at any scheduled or unscheduled visit at or before the Stage 2 Week 24 visit, they will proceed in the study as follows:

- If the participant is deemed a Stage 2 treatment failure as defined in protocol Section 3.2, *Primary Endpoint*, and a corticosteroid injection is deemed sufficient for treatment without new or increased lupus medication, then a blood sample for mechanistic studies will be drawn, the injection will be administered, and the participant will immediately proceed to Stage 3: Re-randomization. (See Section 3.1.3, *Stage 3 Re-Randomization*).
- If the participant is deemed a Stage 2 treatment failure as defined in protocol Section 3.2, *Primary Endpoint*, and a corticosteroid injection is deemed sufficient for treatment without new or increased lupus medication, but the participant refuses the corticosteroid injection, then a blood sample for mechanistic studies will be drawn, and the participant will still immediately proceed to Stage 3: Re-randomization without the corticosteroid injection. (See Section 3.1.3, *Stage 3: Re-Randomization*).

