Participants who do not screen fail at screening will undergo review by a committee of at least two adjudicators. The committee will include the protocol chair and the NIAID medical monitor. The committee will have access to a secure website and will receive an email notification when materials for a potential participant have been uploaded. The review packet will contain a paragraph from the investigator, the EULAR/ACR 2019 criteria, SLEDAI, BILAG, and clinical notes. The investigator will be required to answer the following questions:

1. Is active lupus occurring and can it be classified properly?
2. Is current disease activity sufficient to meet inclusion/exclusion criteria? Here the investigator will justify why they scored lupus disease activity the way they did.
3. Is the participant stable enough to participate in the study? Here the investigator will ensure that the participant does not have organ-threatening disease or is too sick to participate in the study.

The committee will confirm entry criteria. Site investigators will need to be available to answer any questions the committee has within 2 business days.

8.1.2 Evaluation of Eligibility and Randomization for Stage 2

Participants who meet all eligibility criteria and show improvement will proceed with Stage 2 randomization, treatment, visits, and assessments according to Table 8.1, *Stage 1 & 2 Schedule of Events*. See Section 8.2, *Study Procedures and Assessments* for more information on individual clinical and research assessments.

8.1.3 Study-Provided Medication for Stage 2

- Stage 2 study-provided medication (MMF or corresponding MMF placebo) is dispensed to eligible participants at the Stage 2 Randomization Visit after confirmation of participant eligibility and completion of all study visit activities, including corticosteroid injection (if applicable). Dosing begins on the day of randomization.
- Study medication compliance is evaluated at all follow-up visits.
- Refer to Section 3.1.2, *Stage 2 Randomization* for additional information.

8.1.4 Evaluation and Eligibility for Stage 3

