Eligible and consenting participants who have a qualifying Stage 2 treatment failure at or before the Stage 2 Week 24 Visit will immediately proceed with Stage 3 re-randomization according to Table 8.2, *Stage 3 Schedule of Events*. If a qualifying Stage 2 treatment failure is identified after a visit has taken place due to laboratory values, the participant should return for Stage 3 re-randomization within 5 days of discovery of the event. See Section 8.2 *Study Procedures and Assessments* for more information on individual clinical and research assessments.

8.1.5 Study-Provided Medication for Stage 3

- Stage 3 study-provided medication (MMF/voclosporin or MMF/Corresponding placebo for voclosporin) is dispensed to eligible participants at the Stage 3 Re-Randomization Visit. Dosing begins on the day after re-randomization.
- Study medication compliance is evaluated at all following visits.
- Refer to Section 3.1.3, *Stage 3 Re-Randomization* for additional information.

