8.2.2 Clinical Laboratory Assessments

Blood and urine for the clinical laboratory assessments listed below will be collected per Table 8.1, Stage 1 & 2 Schedule of Events and Table 8.2, Stage 3 Schedule of Events. All laboratory assessments will be collected after the participant sees the physician so that appropriate clinical and mechanistic labs can be drawn if the participant is a treatment failure. The results will be evaluated for safety by the site investigator. Abnormal tests that meet grading and reporting criteria will be reported as AEs (See Section 12.3.1, Grading Criteria).

- **Hematology** including complete blood count (CBC) with differential.
- **Blood Chemistry** including complete metabolic panel, eGFR, and creatine kinase PRN.
- **Lipids** (triglycerides and cholesterol).
- **Urinalysis** including dipstick, microscopic, and spot protein-creatinine.
- **TBNK Trucount**
 - For participants who have used B cell depleting therapy within 1 year of screening, CD19+ B Cells will also be evaluated at the Screening Visit.
- **Anti-dsDNA, C3, C4**
- **Immunoglobulin G**
- **Autoantibodies** including Antinuclear Antibody (ANA), Extractable Nuclear Antigen Antibodies (ENA) Panel (Smith Antibody, anti-RNP, Anti-SSA, Anti-SSB), and anticardiolipin antibodies.
- **Infectious Disease Testing (Screening Only)** including HIV Testing, Hepatitis B surface antigen and core antibody (with viral load if indicated), Hepatitis C antibody (with viral load if indicated), and TB Testing.

- **Pregnancy Testing (Women of Child-Bearing Potential Only).** Serum human chorionic gonadotropin (HCG) at screening and then urine pregnancy test at all following visits. First date of last menstrual cycle should also be collected at each visit.
- **SARS-CoV-2 Antigen Testing**

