N. The re-randomization visit should be completed on the date that treatment failure is identified + 5 days.

9 Mechanistic Assays

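### The text requires a pregnancy test at every visit after screening, but Table 8.2 omits it at Stage 3 re-randomization, so a delayed re-randomization can start drug on a test 6 days old or older

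*Combined protocol and SAP*

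**What the plan says.** Two sections set the frequency of pregnancy testing. Section 6.4.2: "Women of childbearing potential will have a pregnancy test at each study visit". Section 8.2.2: "Serum human chorionic gonadotropin (HCG) at screening and then urine pregnancy test at all following visits". Section 8.2.2 also opens with a timing instruction, "Blood and urine for the clinical laboratory assessments listed below will be collected per Table 8.1", and that sentence goes on to name Table 8.2.

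Table 8.1 marks the urine test at every visit from Stage 2 randomization on. Table 8.2 has it from Stage 3 Week 4 on, with nothing at STG3-1 or Week 2.

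On timing, section 3.1.2 says that after a qualifying failure "the injection will be administered, and the participant will immediately proceed to Stage 3: Re-randomization". Note N to Table 8.2 gives an allowance: "The re-randomization visit should be completed on the date that treatment failure is identified + 5 days". For failures found afterwards from laboratory values, section 8.1.4 says "the participant should return for Stage 3 re-randomization within 5 days of discovery of the event". For Stage 3 drug, section 8.1.5 says "Dosing begins on the day after re-randomization"; for Stage 2 drug, section 8.1.3 says "Dosing begins on the day of randomization".

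**The concern.** STG3-1 is where Stage 3 drug is dispensed, and for participants who had MMF placebo in Stage 2 it leads to their first MMF dose. Section 5.1 records embryofetal toxicity as a boxed warning for MMF. A test before dispensing can prevent exposure; a test at Week 4 can only find it afterwards.

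The text and the table give a site two different instructions for this visit, and section 8.2.2 contains both without saying which governs. Neither section 8.1.4 nor the notes to Table 8.2 name a negative result as a condition for dispensing at STG3-1, or ask for a repeat when that visit falls on a later day than the failure visit. Section 3.6 keeps site staff blind to Stage 2 assignment, so a site cannot pick out the participants who are new to MMF and test only them.

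**Working it through.** The plan gives no figure for the age of the test at first dose, so there is none to reproduce. It follows from the schedule.

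**1. Is the blank real?** Table 8.2 has 11 visit columns: STG3-1 to STG3-8, Early Termination, Unscheduled and Safety Follow Up.
- Vital Signs: 1 blank (STG3-1) + 10 marks = 11.
- Urine Pregnancy: 2 blanks (STG3-1, Week 2) + 9 marks = 11.

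The rows line up, so the blanks do not look like an extraction fault.

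**2. Age of the last table-scheduled test at the first Stage 3 dose.** The last such test is at the Stage 2 failure visit. Let L be the days from that visit until failure is identified, D the days from identification to re-randomization (0 to 5, from note N and section 8.1.4), and 1 the day from re-randomization to dosing (section 8.1.5).

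Age = L + D + 1

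| Situation | L | D | Age at first dose |
|---|---|---|---|
| Re-randomized on the day of the failure visit | 0 | 0 | 1 day |
| Failure identified at the visit, full allowance used | 0 | 5 | 6 days |
| Failure found later from laboratory values, full allowance used | L | 5 | L + 6 days |

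The documents do not give L, so the third row is left as a formula.

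**3. Stage 2 for comparison.** The test is marked at STG2-1 and dosing starts that day: 0 days, or about 1 at most if the visit's window of 24 hours either way is used.

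**4. Is the spacing between tests worse?**
- Consecutive Stage 2 visits: 28 + 5 + 5 = 38 days at most.
- Failure visit to Stage 3 Week 4: 5 + 28 + 5 = 38 days at most (plus L where it applies).

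With L = 0 the spacing is the same. What differs is where the test sits relative to the first dose.

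**5. Does the Week 2 blank add a gap?** The first on-drug test is at Week 4 in both stages, at the latest on day 28 + 5 = 33. Someone starting MMF in Stage 3 is tested on drug no later than someone starting it in Stage 2. The text on Week 2 is also unclear: section 6.4.6 counts it as a study visit, section 6.4.7 treats it as an added safety check, and section 3.1.3 describes visits every 4 weeks.

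**6. With a test at STG3-1 on the day drug is dispensed.** Age = 0 + 1 = 1 day, whatever L and D are.

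**The case against.** The strongest reply is that the plan already requires the test. A re-randomization held on a separate day is a separate visit, and two sections then call for testing; a site that follows them has no gap. This stands, and it means the exposure depends on a site preferring the table. It would be tempting to infer that sites will do so, but the documents set no order of precedence.

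A second reply is that the blank has a reason. STG3-1 is laid out as a continuation of the failure visit: examination, vital signs, disease scores and participant-reported outcomes are blank there too. This also stands, and it disposes of the same-day case. Note K, which allows collection at STG3-1 if not already done, does not show that the pregnancy test was forgotten: it covers IgG and the stratification RNA draw, which are not taken at every Stage 2 visit and may need catching up. But the table allows 5 days, and for those days the continuation argument no longer holds.

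A third reply points to the other safeguards: contraception (section 4.2.1), REMS participation (section 12.6.1), menstrual dates recorded at each visit (section 8.2.2), and stopping of study drug on pregnancy (sections 6.4.2, 6.5 and 12.6). A positive test at the failure visit would therefore already bar Stage 3 dosing. These make the risk small. They do not make an earlier test current.

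Two further inferences go too far. One is that participants may start MMF untested: Table 8.1 puts a test at every Stage 2 visit, including the failure visit. The other is that the Week 2 blank is itself a safety gap: steps 4 and 5 show that it leaves Stage 3 starters no worse placed than Stage 2 starters.

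**Conclusion.** The point holds as a conflict between text and table with a limited safety consequence. It should be corrected, but it is not a flaw in the design and does not touch the primary analysis. A site following Table 8.2 after a delayed re-randomization would give the first Stage 3 dose on a test up to 6 days old, against 1 day after same-day re-randomization and 0 days by design in Stage 2. For failures found from laboratory values the limit is 6 days plus the turnaround.

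The 6 days rest on three readings: note N allows any day from 0 to 5, the failure was identified at the visit where the test was done, and the site works from the table. Section 13.7 expects at least 48 former placebo participants in Stage 3, but it would be wrong to turn that into a number at risk. The documents give neither the share of childbearing potential nor the share re-randomized on a later day.

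**What to change.** - **STG3-1.** Mark Urine Pregnancy in Table 8.2 with a note: negative result required before dispensing, unless the test was done the same day at the Stage 2 failure visit. The wording of note K would not do, because a test done at a Stage 2 visit days earlier would satisfy it.
- **Who.** Apply it to all participants of childbearing potential entering Stage 3, because Stage 2 assignment is blinded.
- **Week 2.** Either mark the test at STG3-2, or except the Week 2 safety check in sections 6.4.2 and 8.2.2. This only removes the contradiction.

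The STG3-1 change adds no visit. It costs one urine test for each participant of childbearing potential who is re-randomized on a later day, at a visit she already attends. Marking Week 2 would add one more urine test each at that visit; rewording the two sections would add none.
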